### 1.1.2 Secondary Objectives and endpoints

The secondary objectives of the study are to demonstrate a correlation between the benefit observed on imaging (PET/CT) with:

- reductions in blood eosinophil counts
- improvement in clinic visit lung function
- reductions in fractional exhaled nitric oxide (FeNO)
- improvements in Asthma Quality of Life questionnaire (AQLQ) scores.

The secondary efficacy endpoints are:

- the change from baseline to week 4 in blood eosinophil counts
- the change from baseline to week 4 in FEV1
- the change from baseline to week 4 in FeNO
- the change from baseline to week 4 in AQLQ.

## 1.2. Exploratory/ Safety Objectives and Endpoints

### 1.2.1. Exploratory Objectives and endpoints

Exploratory objectives are:

- to demonstrate a correlation between changes in the lung PET/CT signal produced by reslizumab and serum biological markers of asthmatic inflammation
- to demonstrate a correlation between changes in the lung PET/CT signal produced by reslizumab and other lung function variables including forced vital capacity (FVC), peak expiratory flow rate (PEFR) and forced expiratory flow at the 25% point to the 75% point of forced vital capacity (FEF25%-75%)
- to demonstrate that reslizumab produces greater reductions in inflammation of upper-body lymph nodes and bone marrow than placebo as seen on PET/CT
- for those patients that can produce sputum, to demonstrate an association between changes in sputum eosinophil numbers produced by reslizumab and the lung PET/CT signal produced by reslizumab.

In this study, we wish to determine whether any changes in the levels/quantity of the following biomarkers occur following the administration of reslizumab:

- biological markers of inflammation and asthma (blood):
  - IgE in peripheral blood

- DPP4 in peripheral blood
- 25-hydroxy vitamin D in peripheral blood
- eotaxin-1, -2, and -3 in peripheral blood
- TARC in peripheral blood
- MCP-1 and MCP-4 in peripheral blood
- ILC2 in peripheral blood
- lung function variables:
  - FVC
  - PEFr
  - FEF25%-75%
- the uptake of FDG in the lymph nodes and bone marrow as measured by the PET-CT imaging parameters indicated for the primary efficacy variable.
- sputum eosinophils for those patients that can produce sputum.

Blood samples for assessment of these exploratory biomarkers will be collected and processed using the procedures in place at the investigational center [REDACTED]. For more detailed descriptions, see section 8.1 of the protocol.

### **1.2.2. Safety endpoints**

The safety endpoints are:

- occurrence of adverse events throughout the study
- vital signs (blood pressure, pulse, respiratory rate, body temperature, and blood oxygen saturation (SpO2)) throughout the study
- clinical laboratory evaluations throughout the study
- physical examination findings throughout the study
- use of concomitant medication throughout the study.

## **1.3 Immunogenicity Objectives and Endpoints**

Blood samples for assessment of anti-drug antibodies (ADA) response in Part 2 will be collected from reslizumab-treated patients at scheduled visits at baseline (before dosing, V4) and after dosing at weeks 2 and 6 (visits 5 and 7) only. Unscheduled blood samples for anti-reslizumab antibody assessments will also be collected from reslizumab-treated patients with asthma upon experiencing a severe hypersensitivity reaction (e.g. anaphylaxis).

## 2. STUDY DESIGN

### 2.1. General Design

This is a 7-week, single-center, randomized, double-blind, placebo-controlled, parallel-group study using PET/CT to evaluate the effect of reslizumab administered at 3.0 mg/kg in adult patients with eosinophilic asthma. The study will consist of a screening period (up to 21 days), a 6-week, double-blind treatment/assessment period, and a follow-up telephone contact (7±3 days after last visit).

All subjects who participate in this study will consent at the investigational center [REDACTED] prior to undergoing any study procedures. After consent is obtained, all participants will undergo all tests and procedures required for eligibility, including sputum and blood eosinophil level assessments. Patients with asthma (does not apply to HC subjects) must have a screening blood eosinophil count of  $\geq 400$  cells/ $\mu\text{L}$  to be included. A maximum of 3 screening blood eosinophil assessments will be conducted. If the first assessment yields a blood eosinophil level below 400 cells/ $\mu\text{L}$  patients with asthma may return for a second assessment of blood eosinophil level after 7 days. A third and final assessment will be performed 7 days after the second assessment, if necessary (e.g., if the blood eosinophil level remains  $< 400$  cells/ $\mu\text{L}$  at the second assessment).

The patients must maintain their usual asthma controller regimen without change throughout the screening and study periods. A patient who experiences an asthma exacerbation during this time that requires additional medication, beyond increased SABA use, will be considered to have failed screening and cannot undergo randomization. A patient may be rescreened for this reason 1 time only. If a patient experiences an asthma exacerbation requiring treatment with systemic steroids, they will only be allowed to be rescreened 6 weeks after completion of treatment. All patients that have to be rescreened must be stable on other asthma medications for 30 days prior to rescreening.

This study is designed in 2 parts. Part 1 is a validation step whereby the sponsor wishes to determine (1) the intra-patient reproducibility in the GLG measure, and (2) the difference in the GLG measure between individual patients with severe asthma with an eosinophilic phenotype (1-by-1) and the entire HC group. Limits for both the reproducibility within patients and difference between the 2 groups have been provided by subject matter experts. Part 2 will be a 7-week double-blind evaluation of patients with severe asthma with an eosinophilic phenotype that have been randomized to receive a single dose of either placebo or reslizumab at 3 mg/kg.

#### Part 1

Within 7 days ( $\pm 3$  days) of eligibility being confirmed, participants will have a PET/CT scan as per the PET/CT scan protocol described in Part 2 below. Participants will return to the [REDACTED] 7 days ( $\pm 3$ ) after the first PET/CT scan (taken during visit 2) for a second PET/CT scan following the same procedures described above. HC subjects (n=5) may also have a second sputum induction and blood sample collection at [REDACTED] within 1 day of the second PET/CT scan, if feasible (preferred but not required). Healthy subjects will be considered complete at this time. Only after all 5 HCs have completed the study will patients with asthma be screened.

If the relative difference in GLG (based on the average of the 2 measurements) between healthy subjects and asthma patients will be  $\geq 5\%$ , then the asthma patients will be randomized. A 10%

variability (measured as relative difference between first measurement and second measurement) between PET/CT scans as measured by GLG within each group will be considered as the maximum allowed variability. The Part 1 criteria have been set at these levels to observe a difference between the healthy subjects and patients with asthma and to ensure intra-group reproducibility. The criteria are based on the investigators' prior experience. If these exploratory criteria are not met (i.e., 8 or more asthma patients do not meet the criteria to enter Part 2 [inclusion criteria k and l]), then the study will be reevaluated.

Detailed by-visit information for Part 1 are provided in sections 3.14.1 and 3.14.2 of the protocol.

## **Part 2**

If eligible (i.e., if inter- and intra-group GLG variability criteria are met), patients will be randomized. This may occur at any time after confirmation of eligibility and up to the time of dosing. Patients will return to [REDACTED] for baseline clinical, serological, and biochemical measures at the Clinical Research Center (CRC) according to standard procedures. Once these are completed, patients will randomly receive either placebo or reslizumab and will receive the infusion at [REDACTED]. Any new serious adverse events, reslizumab-related adverse events, and new concomitant medications will be reported.

All planned PET/CT scans (weeks 2, 4, and 6) should be scheduled at the time of randomization. Within 2 weeks ( $\pm 3$  days) of the infusion, patients will return to [REDACTED] for clinical tests and procedures. Within 3 days of this visit, patients will undergo a PET/CT scan at the [REDACTED]. Patients repeat the clinical tests and procedures at weeks 4 and 6 post-infusion. Each visit at [REDACTED] will be followed by a PET/CT scan at the [REDACTED] as described above.

Schematic presentation of the study design for Part 1 and Part 2 is given in Figures 1, 2, and 3, section 3.1 of the protocol.

The assessments and procedures performed during each study visit are detailed in Table 1 below and in Section 3.14 of the protocol. Detailed by-visit information for Part 2 are provided in section 3.14.3 of the protocol. Detailed description of each assessment is provided in section 6 (for efficacy), section 7 (for safety), and section 8 (other assessments) of the protocol.

If a patient elects to withdraw (or is discontinued from treatment by the investigator), every attempt will be made to continue the assessments subsequent to his/her withdrawal from the study (see Table 1 above and section 3.14 of the protocol).

Placebo-Controlled Study–Asthma with Eosinophilia  
Study CEP38072-AS-40105

Statistical Analysis Plan Version 1.0

**Table 1. Study Procedures and Assessments**

Study period	Pretreatment	Phase 1		Phase 2				Follow-up
Visit number	V1 a	V2	V3	V4	V5	V6	V7	V8
Allowed time windows	Up to -21 days	0 days	±3 day(s)	Within 3 days of V3	±3 day(s)	±3 day(s)	±3 day(s)	Up to +7 day(s)
Procedures and assessments	Screening ██████	Baseline (day 1) ██████	W1 (day 7) ██████	Baseline (day 1) ██████	W2 (day 14 from V4)	W4 (day 28 from V4)	W6 (day 42 from V4)/early termination	W7
Informed consent	X	X						
Medical history	X							
Smoking history	X							
Prior medication and treatment history	X							
Complete physical examination b	X						A	
Brief physical examination b				A	A	A		
Vital signs measurement bc	X			A	A	A	A	
Inclusion and exclusion criteria	X	X						
Clinical chemistry bd	X	X	X	A	A	A	A	
Urine/serum β-HCG test for women of child bearing potential bc	X							
Hematology (eosinophils) f	X			A	A	A	A	
Sputum sampling for eosinophils g	X			A	A	A	A	
Urinalysis h	X						A	
PET/CT scan ██████ i		X	X		A	A	A	
ACQ-6 for entry criterion	A							
Electrocardiography b	X							

Placebo-Controlled Study–Asthma with Eosinophilia  
Study CEP38072-AS-40105

Statistical Analysis Plan Version 1.0

Study period	Pretreatment	Phase 1		Phase 2				Follow-up
Visit number	V1 a	V2	V3	V4	V5	V6	V7	V8
Allowed time windows	Up to -21 days	0 days	±3 day(s)	Within 3 days of V3	±3 day(s)	±3 day(s)	±3 day(s)	Up to +7 day(s)
Procedures and assessments	Screening ██████	Baseline (day 1) ██████	W1 (day 7) ██████	Baseline (day 1) ██████	W2 (day 14 from V4)	W4 (day 28 from V4)	W6 (day 42 from V4)/early termination	W7
Spirometry	X			A	A	A	A	
ADA bj				A	A		A	
Blood collection for biomarker analysis				A	A	A	A	
AQLQ				A	A	A	A	
Randomization				A				
Study drug infusion				A				
Adverse event inquiry	X	X	X	A	A	A	A	A
Concomitant medication inquiry	X	X	X	A	A	A	A	A

a Screening visit (visit 1) will take place up to 21 days before the V2 visit. It is understood that not all procedures can be completed on the same day. In particular, the patient may need to return to satisfy the medication hold for screening pre-bronchodilator FEV1.

b Physical examination, vital signs, blood samples, and ECG should be obtained before spirometry procedures and IP administration.

c Vital signs measurements will include blood pressure, pulse, respiratory rate, body temperature, and blood oxygen saturation (SpO2). Height and weight measurements are required only at screening visit.

d The clinical chemistry will include a complete metabolic panel.

e A serum β-HCG pregnancy test will be administered at V1 only, for all participating women of childbearing potential. Urine β-HCG tests will be performed for all participating women of childbearing potential, at V2, V3, V5, V6, and V7, prior to performance of PET/CT scan.

f Hematology will include a complete blood count with differential. The results of the differential blood tests performed after drug administration will be blinded. If there is a medical need to review these results, the investigator will contact the medical monitor.

g The results of the sputum eosinophil assessments performed after study drug administration will be blinded. If there is a medical need to review these results, the investigator will contact the medical monitor.

h A complete urinalysis will be performed at the screening visit, visit 4, and visit 7; a urine dipstick test for glucose will be performed prior to each PET/CT scan.

i Patients should be observed for 1 hour following completion of PET/CT scan.

Placebo-Controlled Study–Asthma with Eosinophilia  
Study CEP38072-AS-40105

Statistical Analysis Plan Version 1.0

j Blood samples for ADA assessment will be collected at baseline (before study drug administration) and other scheduled time points, and upon observation of any severe hypersensitivity reaction (eg, anaphylaxis).

k Randomization can occur any time from determining that the patient qualifies for Part 2 up to study drug infusion. Patient qualification is based on meeting both of the following 2 steps: 1)  $\Delta\text{GLPG} \leq 10\%$  versus V2 [for reproducibility] and 2)  $\Delta\text{GLPG} \geq 5\%$  versus HC [for signal] to study drug infusion.

A=patients with asthma only; ACQ-6=6-item Asthma Control Questionnaire; ADA=anti-drug antibodies; AQLQ=Asthma Quality of Life Questionnaire;  $\beta$ -HCG= beta human chorionic gonadotropin; CBC=complete blood count; CT=computerized tomography; HC=healthy control subjects only; PET=positron emission tomography; V=visit; W=week; X=patients with asthma and healthy control subjects

## 2.2. Randomization and Blinding

This is a randomized, double-blinded, placebo-controlled, parallel-group study. After the 2 baseline PET/CT scans and successful completion of all requirements (Part 1), patients will be randomly assigned 1:1 in a double-blind fashion to receive either placebo or iv 3.0 mg/kg reslizumab. In order to maintain the blind, each patient will be assigned a unique identifier number and all reference to the patient will be by using this identifier.

Patients will be randomly assigned to treatment groups by means of a computer-generated randomization list. The specifications for randomization will be under the responsibility and oversight of Teva Global Statistics. The output of the randomization process will be a patient randomization list.

The sponsor's clinical personnel involved in the study will be blinded to the study drug identity until the database is locked for analysis and the treatment assignment is revealed, with the exception of the bioanalytical group who will not be blinded to facilitate ADA sample analysis and an un-blinded person who will be responsible for randomization assignment. Additionally, in order to maintain the study blind, blood and sputum eosinophil levels assessed after study drug administration will not be available to investigators, their blinded staff, the sponsor, and blinded members of the clinical research organization. There will be un-blinded data management, un-blinded site staff, and an un-blinded CRA who will not sit on the study team and be responsible for un-blinded eosinophil data.

In case of a serious adverse event, pregnancy, or in cases when knowledge of the study drug assignment is needed to make treatment decisions, the investigator may unblind the patient's drug assignment as deemed necessary, mainly in emergency situations. When a blind is broken, the patient will be withdrawn from the study and the event will be recorded on the case report form (CRF). The circumstances leading to the breaking of the code should be fully documented in the investigator's study files and in the patient's source documentation. Treatment assignment should not be recorded in any study documents or source document.

At the time of analysis (after the end of study), after receiving unblinding request from Teva statistician, the service provider will provide the unblinded treatment assignment according to the processes defined in the relevant Standard Operating Procedure (SOP).

## 2.3. Data Monitoring Committee

Data Monitoring Committee will not be used during this study

## 2.4. Sample Size and Power Considerations

This study is exploratory in nature; therefore, no formal hypothesis testing is planned. Based on clinical and practical considerations, 5 healthy subjects and 10 eosinophilic asthma patients (5 patients treated with reslizumab, and 5 patients treated with placebo) is considered adequate for:

1. a validation of the ability of PET/CT to differentiate patients with eosinophilic asthma from HC subjects,
2. an evaluation of the effect of reslizumab versus placebo on inflammation of the lungs.

## **2.5. Sequence of Planned Analyses**

### **2.5.1. Planned Interim Analyses**

There will be no formal interim analysis for this study.

### **2.5.2. Final Analyses and Reporting**

All analyses identified in this Statistical Analysis Plan will be performed after the end of study as defined in the study protocol. This Statistical Analysis Plan and any corresponding amendments will be approved before database lock, in accordance to SOP GBP\_RD\_702 (Statistical Analysis Plan).

The randomization codes will not be unblinded until this Statistical Analysis Plan has been approved and issued.

### **3. ANALYSIS SETS**

#### **3.1.1. Intent-to-Treat Analysis Set**

The intent-to-treat (ITT) analysis set will include all randomized patients (Part 2). In this analysis set, treatment will be assigned according to the treatment to which patients were randomized, regardless of which treatment they actually received. This analysis set will be used for the analysis and summarization of primary efficacy and supportive primary efficacy and secondary efficacy endpoints, for summarization of patients demographics (Summary 15.1.2.2) and patients baseline characteristics (15.1.2.4) for Part 2 and also, for summarization and listing of protocol violations for Part 2 (Summary 15.1.7.2).

#### **3.1.2. Safety Analysis Set**

The safety analysis set will include all patients who receive at least 1 dose of study drug/placebo. In this analysis set, treatment will be assigned based on the treatment patients actually received, regardless of the treatment to which they were randomized.

The safety analysis set will be used for safety analyses of Part 2 of the study. In addition, safety analyses may present safety data from both Part 1 based on all enrolled analysis set (section 3.1.4) and Part 2 of the study based on the safety analysis set, as deemed necessary.

#### **3.1.3. Full Analysis Set**

The full analysis set (FAS) will include all patients in the ITT analysis set who receive at least 1 dose of study drug and have at least 1 post-baseline efficacy assessment. This analysis set will be used for summarization and reporting of all efficacy endpoints and also for exploratory endpoints (Part 2).

#### **3.1.4. Enrolled Analysis Set**

The enrolled analysis set will include all participants enrolled to Part 1 of the study, including healthy subjects and patients with eosinophilic asthma. This analysis set will be used for establishing initial validation of PET/CT scan (Part 1), summarization and reporting of study participants (HCs and patients) disposition (Summary 15.1.1.1), study participants demographics (Summary 15.1.2.1) and baseline characteristics data (Summary 15.1.2.3) of Part 1 and also, for summary and listing of protocol violations for all study participants (Part 1) (Summary 15.1.7.1).

## **4. GENERAL ISSUES FOR DATA ANALYSIS**

### **4.1. General**

Descriptive statistics for continuous variables include n, mean, standard deviation (SD), median, minimum, and maximum.

Descriptive statistics for categorical variables include patient counts and percentages (n, %). Categories for missing data will be presented if necessary.

Correlation will be calculated using Spearman's Rho correlation.

### **4.2. Specification of Baseline Values**

For Part 2, baseline is the last observed data before the first dose of study drug (i.e, Visit 4, Day 1), unless otherwise noted. For assessing changes from baseline in PET/CT signal as surrogate of lung inflammation in patients with asthma at each post-randomization visit, the baseline is the average of two measurements at visits 2 and 3 of Part 1. See Table 1 (section 2.1).

### **4.3. Handling Withdrawals and Missing Data**

Overall mean scores for AQLQ (Asthma Quality of Life Questionnaire at each visit of Part 2) and ACQ-6 (6-item Asthma Control Questionnaire for entry criterion at Screening for patients with asthma only) will be calculated for patients who answer all the questions. For the item analysis, the mean of the score by domain will be computed if all questions of the domain are answered.

For the AQLQ questionnaire, if a lot of missing data are observed, it will be dealt with by imputing mean values where more than half of the responses to a subscale will be present, as sensitive analysis (Apfelbacher et al. 2012).

For all other variables, only the observed data from the evaluable patients/subjects up to study completion or study withdrawal will be used in the statistical analyses, i.e., there is no plan to impute missing data for other variables.

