### **6.3.4. AQLQ score**

#### **6.3.4.1. Definition**

The fourth secondary efficacy endpoint is change from baseline (Day 1/Visit 4) to weeks 2, 4 and 6 in AQLQ.

The AQLQ+12 is a modified version of the standardized self-administered AQLQ questionnaire, which was developed to measure functional impairments experienced by adults  $\geq 17$  years of age. The AQLQ+12 is valid for patients aged 12 to 70 years and includes 32 questions/items in 4 domains: asthma symptoms (12 questions: 6, 8, 10, 12, 14, 16, 18, 20, 22, 24, 29, 30), activity limitation by asthma (11 questions: 1 to 5, 11, 19, 25, 28, 31, 32), emotional function (5 questions: 7, 13, 15, 21, 27) and exposure to environmental stimuli (4 questions: 9, 17, 23, 26). Patients are asked to recall their experiences during the previous 2 weeks and score their response options to each of the questions on a 7-point scale where 7 = no impairment and 1 = severe impairment.

The questionnaire is analyzed directly from the scores recorded. First, the overall AQLQ score is calculated as the mean of all 32 responses for each patient and the individual domain scores are the means of the responses within each domain for each patient. For details of the AQLQ+12 questionnaire, see Appendix B of the protocol and Juniper et al (1992).

AQLQ scores were recorded at Visits 4 (Baseline, Day 1), 5, 6 and 7 of Part 2 (see Table 1).

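### One blank among 32 AQLQ items voids the overall score for that visit, with 5 patients per arm; the rule that would keep it is only a sensitivity analysis with an undefined trigger

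*SAP*

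**What the plan says.** AQLQ is a secondary efficacy endpoint, defined as "the change from baseline to week 4 in AQLQ" (SAP 1.1.2). SAP 6.3 also correlates it with the week-4 change in GLG by Spearman's rho. SAP 6.3.4.2 summarizes the overall score and each domain.

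SAP 6.3.4.1 says that the instrument "includes 32 questions/items in 4 domains" and that "the overall AQLQ score is calculated as the mean of all 32 responses for each patient". On timing it says "AQLQ scores were recorded at Visits 4 (Baseline, Day 1), 5, 6 and 7 of Part 2".

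SAP 4.3 sets the handling of blanks:

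- Overall mean scores "will be calculated for patients who answer all the questions".
- For domains, "the mean of the score by domain will be computed if all questions of the domain are answered".
- The alternative is "imputing mean values where more than half of the responses to a subscale will be present, as sensitive analysis", used "if a lot of missing data are observed".

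No count or percentage defines the trigger, and no person or time is named for judging it. The SAP also does not say whose mean is imputed: the patient's own subscale mean or a group mean.

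**The concern.** The main scoring rule discards a 32-item overall score for a single blank, and a change score needs two complete forms. In a trial planned with 5 patients per arm, each discarded change score is a large share of the data. Yet one blank item carries very little of the overall score.

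The trigger is a separate weakness. How much is missing can be judged only on the observed data, and SAP 4.3 does not require this to be done blinded. Two statisticians could both follow the SAP, and one would report the imputed analysis while the other would not.

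**Working it through.** **Item count.** The four item lists in SAP 6.3.4.1 contain 12 + 11 + 5 + 4 = 32 items and cover numbers 1 to 32 once each. The stated 32 is reproduced.

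**What one blank removes under the main rule.** AQLQ is recorded at visits 4, 5, 6 and 7; visit 6 is week 4.

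| Visit of the blank | Overall change scores lost | Domain change scores lost |
|---|---|---|
| 4 (only baseline) | weeks 2, 4 and 6 | affected domain, all weeks |
| 6 (week 4) | week 4 | affected domain, week 4 |
| 5 or 7 only | week 2 or week 6; week 4 intact | affected domain, that week |

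**Cost of one lost patient.** It is 1/5 = 20% of an arm. It is also 1 of 10 pairs for Spearman's rho if the arms are pooled. With equal SDs in the two arms, the standard error of the difference relative to 5 vs 5 is √(1/n₁ + 1/n₂) / √(2/5):

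- 4 vs 5: 0.6708 / 0.6325 = 1.06
- 4 vs 4: 0.7071 / 0.6325 = 1.12
- 3 vs 5: 0.7303 / 0.6325 = 1.15

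**How often it could happen.** The documents give no item skip rate, so q below is an assumption, with skips independent across items and visits.

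- Share of forms lost = 1 − (1 − q)^32.
- Week-4 overall change available = (1 − q)^64, from 32 items at visit 4 and 32 at visit 6.
- More-than-half rule: at least 7 of 12, 6 of 11, 3 of 5 and 3 of 4 items answered. The four binomial tail probabilities are multiplied, then squared for the two visits.

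| q | Forms lost | Week-4 change available | Expected of 10 without it, all-items rule | Expected of 10 without it, more-than-half rule |
|---|---|---|---|---|
| 0.1% | 3% | 0.938 | 0.6 | 0.0001 |
| 0.25% | 8% | 0.852 | 1.5 | 0.0008 |
| 0.5% | 15% | 0.726 | 2.7 | 0.003 |
| 1% | 28% | 0.526 | 4.7 | 0.012 |

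**What the more-than-half rule gives up.** Items run from 1 to 7, so one blank filled with a mean is wrong by at most 6 points.

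- Overall score, one blank: at most 6/32 = 0.19 points.
- Environmental domain (4 items), one blank: at most 6/4 = 1.5 points on that domain score.
- Fewest answered items that still give an overall score, if every domain must be scorable: 7 + 6 + 3 + 3 = 19 of 32, so up to 13 blanks.

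**The case against.** The case for leaving the rule alone has real parts.

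- **The loss is narrower than it may look.** A reader might infer that one skipped item drops the patient from the AQLQ endpoint altogether. The documents do not support that: domains are scored and reported separately, and a blank at visit 5 or 7 leaves the week-4 change untouched. This stands.
- **The frequency is assumed.** A reader might take the table as a forecast of several lost patients. It is not one. Blanks clustered in a few patients would cost fewer of them. The questionnaire is given at clinic visits at one center, and Protocol 13.2 has case report forms checked for completeness and mandatory values. The documents do not say whether blanks are prevented, so the loss could be near zero. This stands.
- **Complete-form scoring is defensible.** It fits the definition of the overall score as a mean of 32 responses and the default in Protocol 9.3.1 against imputation. By its title, the one source cited for the half rule concerns a short form of the AQLQ and another asthma questionnaire, not the AQLQ+12. Preferring the half rule is a judgement, since neither document ranks the two. But the protocol default yields where something else is specified, and the SAP Introduction lets the SAP prevail, so nothing bars the change.
- **Little depends on it.** A reader might infer a threat to error control, or that the vague trigger could replace the main result. Neither follows. SAP 2.4 plans no hypothesis testing, SAP 6.3 uses no inferential statistics, and the trigger governs only an added analysis.

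**Conclusion.** The point holds within these limits. Under SAP 4.3 a single blank voids the overall AQLQ score for that visit and the score of the affected domain. A blank at visit 4 or visit 6 removes the patient's week-4 overall change. Each patient lost is 20% of an arm and adds about 6% to the standard error of the arm difference, assuming equal SDs.

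The number of patients affected is unknown. The figure of about 0.6 to 4.7 of 10 rests wholly on assumed independent skips at 0.1% to 1% per item. The undefined trigger and the unnamed mean are gaps whatever the skip rate.

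The harm is lost information and avoidable discretion in a descriptive secondary analysis. This is a cheap improvement of low severity.

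**What to change.** Reword SAP 4.3 as follows:

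- **Main scoring:** score a domain when more than half of its items are answered, as the patient's own mean of the answered items in that domain at that visit. Compute the overall score when every domain is scorable, with blanks filled by that same domain mean.
- **Sensitivity analysis:** always report complete-form scoring.
- **Trigger:** delete the condition "if a lot of missing data are observed".
- **Reporting:** give the number of incomplete forms scored, by arm and visit, and the number of blanks in each.

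If complete-form scoring is kept as the main rule, the minimum is to run the half-rule analysis always, or give its trigger a number, and to name the mean that is imputed.

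The cost is a few sentences in the SAP, with no change to data collection. The downside is more item-level noise. It is small for one blank in the overall score, but larger for forms near the 19-item limit and for the 4-item environmental domain. The complete-form results alongside would show whether it matters.
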